Earlier concepts of MS disease pathology have suggested that pathogenic T cells are sufficient for the full expression of MS. However, it is now evident that full autoimmune B cells and humoral immune mechanisms also play key roles.⁵ Ocrelizumab is a humanized monoclonal antibody that targets CD20 and selectively depleted CD-20 expressing B cells. CD20 is a B cell surface molecule that is expressed on pre B cells and mature B cells, but not expressed earlier in the development of B cells or on mature plasma cells. In all three ocrelizumab studies (with relapsing and progressive populations), treatment with 600 mg of ocrelizumab led to rapid and complete depletion of circulating CD19⁺ B cells within 14 days post treatment.⁴ B cell depletion was sustained throughout treatment period. The median time to repletion of B cells was 72 weeks (range 27-175 weeks). We hypothesize that in switching rituximab treated patients to ocrelizumab, the proportion of patients with B cell depletion (CD19⁺ and CD20⁺ ≤ 1%) 6 months after the first and third infusion of ocrelizumab will be the same as the baseline assessment which will be 6 months after the last dose of rituximab and similar to findings in OPERA I and II.

Immunogenicity results from the OPERA I and II trials examined the number of patients who had treatment induced anti-drug antibodies (ADA) to ocrelizumab.⁴ Of the 807 patients who received ocrelizumab and had an ADA assay from a post baseline sample during the controlled treatment period, 3 patients (0.4%) showed treatment induced ADA to ocrelizumab. Of these, 1 patient tested positive for neutralizing antibodies (NAB) to ocrelizumab. During the open label extension phase, the prevalence of ADA continued to remain low with post baseline incidence of 1.9% (2/103 with treatment induced ADA). Currently there is little evidence examining the prevalence of treatment induced ADAs to both rituximab and ocrelizumab in patients that switch from the former to the latter in comparison to continuing rituximab patients. Therefore, we will perform assays to detect ADAs to both rituximab and ocrelizumab in all patients switching from rituximab to ocrelizumab at Day 1, 6 months and between 12 and 18 months on ocrelizumab.

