2.2 Secondary Objectives

Secondary Objective: Our secondary objective is to assess the impact of switching from rituximab to ocrelizumab (**only in the switching group**) on the incidence and prevalence of anti-drug antibodies to ocrelizumab. The presence of anti-drug binding antibodies will be assessed prior to the first and third ocrelizumab infusion and six to twelve months after the last ocrelizumab infusion. The serum drawn before the first infusion of ocrelizumab will be the baseline comparator since these patients will only have been exposed to at least two rituximab infusions over 6 months with no prior exposure to ocrelizumab. This means we will have 100 serum samples prior to ocrelizumab exposure and 200 after ocrelizumab exposure. These assays will be performed by PPD Bio A

Laboratories (in Richmond, VA) who will assess the anti-drug antibodies to ocrelizumab”, and “QPS (Netherlands) who will assess the anti-drug antibodies to rituximab as a single batch once all samples have been collected and cryopreserved.

Other secondary objectives that will be assessed in **the switching group** only include the following:

- a. We will assess the percent of ocrelizumab treated patients that exhibit early recovery of CD19+ and/or CD20+B cells (>1%) prior to each ocrelizumab infusion and at month 12 or 18 which is 12 or 18 months following the first infusion of ocrelizumab. We will compare this to the percent of patients with evidence of early recovery from rituximab as assessed by the baseline B cell panel. Our test will also identify CD19 antigen expression to confirm depletion since presence of anti-CD 20 MAB in patients blood may confound the CD-20 expression assay.
- b. We will assess cytokines to evaluate for possible contribution of a cytokine storm to infusion reactions. Cytokines will be assessed using the MesoScale platform. These blood samples will be collected before the start of each ocrelizumab infusion and following infusion completion. Blood samples will also be collected during a moderate or serious IRR.
- c. We will describe all adverse events and serious adverse events in addition to IRRs (for example infections) as described in the investigator’s brochure.

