For patients who are switching to ocrelizumab, the first dose of ocrelizumab will be a split dose of 300 mg on day 1 and day 15 followed by 600 mg, six months later as approved by the FDA. The timing of 12 month dose may be delayed due to vagaries in the approval of biologics by third payors. Therefore, we will include data from patients at the T3 visit between the month 12 and 18 after starting ocrelizumab. Standard of care rituximab doses are 1000 mg given as first dose followed by 500mg (or 1000 mg if evidence of early B cell recovery) every 6 months thereafter. Study patients will be current patients of the RMMSC who meet the inclusion criteria and are currently receiving rituximab infusions from the University of Colorado Hospital's Outpatient Infusion Center. Analysis of IRRs will be conducted by the research team at RMMSC. Anti-drug antibody analysis will be conducted by two external vendors: PPD Bio A Laboratories, Richmond, VA will conduct the anti-drug antibodies assays for ocrelizumab, QPS Netherlands, Netherlands will conduct the anti-drug antibodies assays for rituximab using cryopreserved blood samples sent by the RMMSC research team as a single batch at the end of the study. Cytokine analysis will be conducted by personnel at the biobank repository at RMMSC. Study duration, including the recruitment (estimated to take 6 months), data analysis and manuscript development is anticipated to be 24 months.

The study design is represented in **Figure 1** below and described in further detail in section 4.5.1

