3.3.2 Secondary Outcome Measures

- a. Anti-drug antibodies (ADAs): We will measure the number of patients who have treatment induced ADAs against rituximab and ocrelizumab prior to every ocrelizumab infusion (T_0 , T_1 , T_2) and at the research termination visit (T_3 =between month 12 and 18) in **ONLY** the switching group. This analysis will be performed by PPD Bio A Laboratories (in Richmond, VA) who will assess the anti-drug antibodies to ocrelizumab, and “QPS (Netherlands) who will assess the anti-drug antibodies to rituximab a single batch at end of study for the switching group.
- b. Treatment efficiency: We will measure B cell depletion before each ocrelizumab infusion (T_0 , T_1 and T_2), by the clinical laboratories (T cell and B cell panel) at the University of Colorado Hospital. We will measure the proportion of patients who are B cell depleted (CD-19+ and CD-20+) by the time of the next infusion and 6 to 12 months after the last infusion in the switching group.
- c. Cytokine profile: To better characterize infusion reactions and evaluate the contribution by either hypersensitivity reactions to ocrelizumab directly and/or by release of cytokines from dying CD20 positive cells, serum levels of cytokines will be evaluated. Cytokines will be measured using the MesoScale platform before the start of each ocrelizumab infusion, and after the infusion is completed (T_0, T_1, T_2, T_3). In addition, blood samples will be collected for those who experience a moderate to severe IRR to further examine cytokine profiles during an IRR. Plasma samples will be analyzed using the V-PLEX Human Biomarker 40-Plex Kit which assays for IFN- γ , IL-1 β , IL-2, IL-4, IL-6, IL-8, IL-10, IL-12p70, IL-13, TNF- α , GM-CSF, IL-5, IL-16, IL-7, IL-12/IL-23p40, IL-1 α , VEGF-A, IL-17A, IL-15, TNF- β , IL-8 (HA), MCP-1, MCP-4, Eotaxin, IP-10, MDC, Eotaxin-3, TARC, MIP-1 α , MIP-1 β , VEGF-C, VEGF-D, Tie-2, Flt-1/VEGFR-1, PIGF, FGF (basic), SAA, CRP, VCAM-1, ICAM-1 per manufacturer’s recommendation on a MesoScale SECTOR Imager 2400. This array of cytokines will provide information on the levels of cytokines being released during the infusion to determine if they are limited to those released by B cells. Patients will be categorized as either not having had an IRR (Grade 0), having had a mild

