4.1.2 Inclusion Criteria

Switching group:

- Current active patient of RMMSC
- 18-65 years
- Diagnosis of relapsing forms of MS
- Completed **≥ two doses** of rituximab with the last dose having been administered:
 - a) within 12 months of screening
 - and
 - b) at least 6 months prior to first planned infusion of study drug
- Are receiving their current infusions of rituximab at the University of Colorado Outpatient Infusion Center
- Have discussed the possibility of switching to ocrelizumab with their MS provider
- Screened for Hepatitis B and C and TB within 2 years of first dose of ocrelizumab
- A negative serum pregnancy test must be available for premenopausal women and for women <12 months after the onset of menopause, unless they have undergone surgical sterilization.
- Women of childbearing potential must agree to use a “highly effective”, hormonal form of contraception or two “effective” forms of non-hormonal contraception. Contraception must continue for the duration of study treatment and for at least three months after the last dose of study treatment
- Are able to complete patient reported outcomes developed as English written scales.
- Must be able and willing to give meaningful, written informed consent prior to participation in the trial, in accordance with local regulatory requirements

Comparator group:

- Current active patient of RMMSC

- 18-65 years
- Diagnosis of relapsing forms of MS
- Completed \geq **two doses** of rituximab with the last dose having been administered within 12 months of screening as standard of care
- Are receiving their current infusions of rituximab as standard of care at the University of Colorado Outpatient Infusion Center and will continue to do so
- Are willing to be followed for subsequent rituximab infusions during the study period as standard of care, and/or allow retrospective data collection on previous rituximab infusions
- Must be able and willing to give meaningful, written informed consent prior to participation in the trial, in accordance with local regulatory requirements

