Standard of care rituximab doses are 1000 mg given as first dose followed by 500mg (or 1000 mg if evidence of early B cell recovery) every 6 months thereafter. However, [The B cell depletion with rituximab can last up to two years in some patients with good efficacy demonstrated after a single dose in the HERMES study for up to a year.³](#) Patients are often out of window due to difficulties in obtaining insurance approval within the 6 month time window. Therefore, we will include those patients that receive rituximab infusions within a 12 month window.

Although ocrelizumab may be administered on an outpatient basis, patients may be hospitalized for observation at the discretion of the investigator. Ocrelizumab infusions should always be administered in a hospital or clinic environment under close supervision of the investigator or a medically qualified staff member. Each ocrelizumab infusion should be given as a slow IV infusion over approximately 150 minutes (2.5 hours) for the 300-mg dose. To reduce potential Infusion Related Reactions (IRRs), all patients will receive prophylactic treatment with 100 mg of methylprednisolone (or equivalent IV steroid), administered by slow IV infusion, to be completed approximately 30 minutes before the start of each ocrelizumab infusion.

It is also strongly recommended that the infusion is accompanied by prophylactic treatment with an analgesic/antipyretic such as acetaminophen/paracetamol (1 g) and/or an IV or oral antihistamine (such as IV diphenhydramine 50 mg or equivalent dose of alternative) 30 – 60 minutes prior to the start of an infusion to reduce potential IRRs. Patients administered a sedating antihistamine for the treatment or prevention of IRRs should be given appropriate warnings concerning drowsiness and potential impairment of ability to drive or operate machinery.

Since transient hypotension may occur during ocrelizumab infusion, the investigator may wish to withhold anti-hypertensive medications 12 hours prior to ocrelizumab infusion.

Ocrelizumab must not be administered as an IV push or bolus. Well-adjusted infusion pumps should be used to control the infusion rate, and ocrelizumab should be infused through a dedicated line. It is important not to use evacuated glass containers (to prepare the infusion), which require vented administration sets, because this causes foaming as air bubbles pass through the solution.

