The Patient-Determined Disease Steps (PDDS) is a PRO version of the clinician-reported EDSS which hones the stages of cane use and thus is more responsive to mid-range disability changes.⁸ This tool asks the patient to characterize level of disability into one of nine steps (0=normal, 1=mild disability, 2=moderate disability, 3=gait disability, 4=early cane, 5=late cane, 6=bilateral support, 7=wheelchair scooter, 8=bedridden). The PDDS will be used to characterize (and to control for) disability in both study groups at all study time points.

Following the screening visit, patients in the switching group will be scheduled for their first infusion of ocrelizumab at their next regularly scheduled infusion date (no more than six months after their last rituximab infusion). Study infusion cycle T₁ will have an acceptable window of +/- 4 days since it is given 15 days apart, while infusion cycles T₂ and T₃ will have an acceptable window of +/- 14 days since it is administered 6 months later.

Prior to the start of the infusion, blood samples will be collected that will be utilized for several purposes. At infusion cycle time points, T₀, T₂ and T₃ blood samples for the following assessments will be drawn. First, patients will be

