5.2 Methods and Timing for Assessing and Recording Safety Variables

The investigator is responsible for ensuring that all AEs and SAEs that are observed or reported during the study, are collected and reported to the FDA, appropriate IRB(s), and Genentech, Inc. in accordance with CFR 312.32 (IND Safety Reports).

Adverse Event Reporting Period

The study period during which all AEs and SAEs must be reported begins after informed consent is obtained and initiation of study treatment or "initiation of any study procedures" and ends at T₃ which is 6 months after last dose of study medication. After this period, investigators should only report SAEs that are attributed to prior study treatment.

Assessment of Adverse Events

AEs and SAEs may be collected from medical record review, or elicited by asking non-directive questions at each study visit both before and after the infusion. Infusion-related AEs will be captured by the infusion nurses as well as self-reported by the patient as described in Outcome Measures. Patients will also be reminded to alert the study team about any concerning health issues between study visits. Each recorded AE or SAE will be described by its duration (i.e., start and end dates) and will include, and actions taken.

For all recorded AEs, a study investigator will make an assessment of seriousness, and causality. To ensure consistency of AE and SAE causality assessments, investigators should apply the following general guideline:

Yes

There is a plausible temporal relationship between the onset of the AE and administration of the ocrelizumab, and the AE cannot be readily explained by the subject's clinical state, intercurrent illness, or concomitant therapies; and/or the AE follows a known pattern of response to the ocrelizumab; and/or the AE abates or resolves upon discontinuation of the ocrelizumab or dose reduction and, if applicable, reappears upon re-challenge.

No

Evidence exists that the AE has an etiology other than the ocrelizumab (e.g., preexisting medical condition, underlying disease, intercurrent illness, or concomitant medication); and/or the AE has no plausible temporal relationship to ocrelizumab administration (e.g., event diagnosed 2 days after first dose of ocrelizumab).

Expected adverse events are those adverse events that are listed or characterized in the Package Insert or current Investigator Brochure.

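### The B-cell recovery comparison with the rituximab baseline does not align time since last infusion, and the timing rules conflict, so an interval difference could be read as a drug difference in either direction, chiefly at T3

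*Combined protocol and SAP*

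**What the plan says.** **The comparison.** Section 2.2, item a, measures early recovery (CD19+ and/or CD20+ above 1%) before each ocrelizumab infusion and at month 12 or 18, in switchers only. The comparator is their own baseline panel: "We will compare this to the percent of patients with evidence of early recovery from rituximab as assessed by the baseline B cell panel".

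**The intent.** The Introduction hypothesises that the depleted proportion "6 months after the first and third infusion of ocrelizumab will be the same as the baseline assessment which will be 6 months", with that baseline counted from the final rituximab dose. That is a contrast at equal intervals.

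**The rituximab-to-ocrelizumab interval.**
- Section 4.1.2: last rituximab within 12 months of screening and "at least 6 months prior to first planned infusion of study drug".
- Section 4.5.1: first ocrelizumab "no more than six months after their last rituximab infusion".
- Section 4.3.1: "Patients are often out of window due to difficulties in obtaining insurance approval within the 6 month time window", so a 12-month window between rituximab infusions is accepted.

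**T3.**
- Section 3.1: "we will include data from patients at the T3 visit between the month 12 and 18 after starting ocrelizumab", because payer approval may delay the 12-month dose. Section 4.5.1 and Table 1 give the same 12 to 18 months.
- Section 3.3.2, item b: "6 to 12 months after the last infusion in the switching group".
- Section 5.2: "which is 6 months after last dose of study medication".

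**T1 (Day 15).** Sections 2.2 and 3.3.2 imply a B-cell sample before this infusion. The section 4.5.1 text and Table 1 schedule B-cell panels at T0, T2 and T3 only.

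**The analysis.** Section 4.9.4 lists the proportion with depleted B cells as a secondary endpoint, sets alpha at 0.05 for all tests, and extends GEE or GLMM to other longitudinal binary outcomes. The covariates it names are demographic and disease variables. Interval since infusion is not among them. Section 3.1 calls B-cell reconstitution exploratory.

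**The concern.** The chance of having recovered B cells rises with time since the last anti-CD20 infusion. The Introduction itself reports complete depletion within 14 days and repletion at a median of 72 weeks (range 27 to 175). A comparison of recovery on two drugs is therefore informative about the drugs only if samples are taken at similar intervals, or if the analysis accounts for the difference. The intended contrast is matched; the one written in section 2.2 is not.

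The direction depends on which samples run late. Late T3 samples against six-month baselines count against ocrelizumab. Late baselines shrink or reverse that gap and make ocrelizumab look better at T2. Section 3.2 names efficiency of B-cell depletion as one of three questions the study has good power to address, and says unproven claims of superiority on it will influence patients, prescribers and payers. An interval artefact here would feed that debate.

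**Working it through.** **The plan's own figure.** There is none for this endpoint: no expected rate, sample size or power calculation. The only power calculation (section 4.9.6: 34.3% v 14.3%, 95 per group, two-sided 0.05) concerns infusion reactions. It reproduces at 90.1% against the stated 90% and does not bear on this point.

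**Step 1. Baseline rules.** At least six months (4.1.2) and no more than six months (4.5.1) agree only at exactly six months.

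**Step 2. Intervals on ocrelizumab.** Month = 28 days and visit windows from section 4.5.1.
- T2 minus the Day 15 infusion: 168 - 14 = 154 days, or 22 weeks. With windows: (168 - 14) - (14 + 4) = 136 to (168 + 14) - (14 - 4) = 172 days, or 19.4 to 24.6 weeks.
- T3 minus the T2 infusion: 336 - 168 = 168 to 504 - 168 = 336 days, or 24 to 48 weeks. With windows: (336 - 14) - (168 + 14) = 140 to (504 + 14) - (168 - 14) = 364 days, or 20 to 52 weeks.

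Without assuming any curve: every in-window T2 sample precedes the earliest reported repletion (27 weeks), while the T3 range straddles it.

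**Step 3. Illustration with no drug difference.** Assume one lognormal time-to-recovery curve for both drugs, median 72 weeks, with 27 weeks placed at the 0.1st to 2nd percentile. Then F(t) = Φ(ln(t/72)/σ) and σ = ln(72/27)/z, so σ runs from 0.981/3.090 = 0.317 to 0.981/2.054 = 0.478. Percentage recovered, low to high curve:
- 22 weeks: 0.01 to 0.65
- 24 weeks: 0.03 to 1.07
- 36 weeks: 1.45 to 7.33
- 48 weeks: 10.1 to 19.8
- averaged evenly over 24-36 weeks: 0.44 to 3.63
- averaged evenly over 24-48 weeks: 2.67 to 8.39

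Gap = ocrelizumab minus baseline, in percentage points, both taken from the same curve. A positive gap counts against ocrelizumab. The timing mixes are assumptions.

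| Ocrelizumab sample | Rituximab baseline | Spurious gap |
|---|---|---|
| T2 at 22 weeks | all at 24 weeks | -0.02 to -0.4 |
| T2 at 22 weeks | half at 24, half at 36 | -0.7 to -3.6 |
| T3 even over 24-48 | all at 24 | +2.6 to +7.3 |
| T3 half at 24, half even over 24-48 | all at 24 | +1.3 to +3.7 |
| T3 even over 24-36 | all at 24 | +0.4 to +2.6 |
| T3 even over 24-48 | half at 24, half at 36 | +1.9 to +4.2 |
| T3 even over 24-48 | all at 36 | +1.1 to +1.3 |
| T3 even over 24-48 | spread like T3 | 0 |
| T3 at 24 | half at 24, half at 36 | -0.7 to -3.1 |

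Example (third row, high curve): 8.39 - 1.07 = 7.3. Example (last row, high curve): 1.07 - (1.07 + 7.33)/2 = -3.1.

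**Step 4. Sensitivity to the curve.** Keeping the median at 72 weeks but assuming 5% recovered at 24 weeks, the third row becomes 15.3 - 5.0 = 10.3 points. The size follows the assumed curve, which the documents do not supply at the 1% threshold.

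**The case against.** The strongest reply has four parts.

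1. **Late baselines offset late T3 samples.** This stands. A reader might infer from the T3 window that the plan is biased against ocrelizumab. The documents do not support that: sections 4.1.2 and 4.3.1 allow late baselines too, and the table shows the gap shrinking, vanishing or reversing. Section 3.1 also presents T3 lateness as a possible payer delay, so an even spread over 24 to 48 weeks is an assumption near the unfavourable end.

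2. **The T1 sample is an editorial slip.** This stands. A reader might infer that a Day 15 sample will flatter ocrelizumab. The section 4.5.1 text and Table 1 agree that no B-cell panel is drawn then, so if they govern there is no such comparison.

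3. **The T3 rules are less divided than they look.** Mostly right. Sections 2.2 (antibody timing), 3.1, 3.3.2, 4.5.1 and Table 1 agree on 12 to 18 months, or 6 to 12 months after the last infusion. The six months in section 5.2 belongs to adverse-event reporting. Settling on the wider window, however, keeps the mismatch with a six-month baseline.

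4. **The endpoint is exploratory, presented descriptively, and partly pragmatic.** In part. Section 3.3.2 does measure depletion by the next infusion, whenever that falls. But section 4.9.4 also provides for testing at 0.05, and section 3.2 claims good power on this question without a calculation. A descriptive contrast across unequal intervals can still be misread.

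A reader might also carry the concern over to the primary infusion-reaction endpoint; nothing in the documents shows it to be affected.

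**Conclusion.** The point holds in a limited form. As written, the plan compares recovery at unequal and partly contradictory intervals, contrary to its own six-month hypothesis, and has no step that would separate interval from drug. The exposure is chiefly at T3. T0 v T2 is nearly matched if baselines really are at six months, and drifts in ocrelizumab's favour if they are late.

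Neither size nor sign can be fixed. The illustrative T3 range of about -3 to +7 points rests on a common lognormal curve, the 27-week anchor, the assumed timing mixes, and treating the Introduction's undefined repletion as equivalent to recovery above 1%. This is worth correcting before analysis, at the weight of a secondary or exploratory endpoint.

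**What to change.** 1. Reconcile sections 4.1.2 and 4.5.1 into one rituximab-to-ocrelizumab interval rule, and align section 5.2 with the 12 to 18 month T3 window.
2. Derive weeks since the last anti-CD20 infusion at every B-cell sample: last rituximab for T0, the Day 15 infusion for T2, the T2 infusion for T3.
3. Make T0 v T2 within a common window of about six months the main contrast, and report how many baselines fall outside it. A 19 to 28 week window is one choice; the limits are a judgement.
4. Present T3 by interval since the T2 infusion (for example 20-28, 29-40 and over 40 weeks). Compare it with baseline only within matching intervals, and otherwise leave it descriptive.
5. As an editorial correction, remove the T1 B-cell sample from sections 2.2 and 3.3.2 to match section 4.5.1 and Table 1.

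**Cost.** Wording, plus one variable derived from infusion dates. No in-window T2 sample is lost under a 19 to 28 week window. Late baselines leave the main contrast; their number is not given, so the loss of precision is unknown. Few events are expected at six months: on the illustrative curves about 0 to 1 per 100 at both T0 and T2, so the contrast can exclude a large difference but will not detect a small one.

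**Gain.** On the same curves, restricting the half-late case to its 24-week baselines cuts the T2 gap from 0.7-3.6 points to 0.02-0.4. Baselines spread evenly over 24 to 28 weeks would leave 0.1-1.0, and the extreme pairing in the window (28 v 19.4 weeks) 0.1-2.1. Alignment removes only the interval component: T2 still follows more cumulative anti-CD20 exposure, and the rituximab dose varies (section 3.1).
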